| 4.7 | NA | NA | Pharmacokinetic | 201585/primary_02/T4.6 | Summary of Results of Steady State Assessment by Strata for Q8W Arm- Evaluable Concentration | Display by rederived randomization strata and add footnote for strata. For Q8W arm only. | W48 | |
| NA | 4.7 | NA | Pharmacokinetic | Shell PK_T1 | Summary of Expected and Missed Visits by Strata and Treatment (Maintenance Phase) – Plasma CAB PK Concentration | | W96 | |
| NA | 4.8 | NA | Pharmacokinetic | Shell PK_T1 | Summary of Expected and Missed Visits by Strata and Treatment (Maintenance Phase) – Plasma RPV PK Concentration | | W96 | |
| NA | 4.9 | 4.1 | Long-term Follow-up | 207966/primary_02/T4.1 | Summary of Plasma CAB PK Concentration (ug/mL) -Time Data by Treatment and Visit (Long-term Follow-up Phase) - Including Log-transformed Statistics | Remove the column 'Pl. Time' and the second footnote. Produce only if we have additional LTFU storage samples planned to be analysed since last analysis data cut. | W96, EOS | |
| NA | 4.10 | 4.2 | Long-term Follow-up | 207966/primary_02/T4.2 | Summary of Plasma RPV PK Concentration (ng/mL) -Time Data by Treatment and Visit (Long-term Follow-up Phase) - Including Log-transformed Statistics | Remove the column 'Pl. Time' and the second footnote. Produce only if we have additional LTFU samples planned to be analysed since last analysis data cut. | W96, EOS | |

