| | | | Follow-up | F4.15 | Last Injection Plots by Strata | treatment instead of by strata and change "Strata" to be "Treatment" in the title; Color-code different strata of prior exposure; exclude RPV concentrations on/after the start of LTFU oral RPV and add footnote for this exclusion; will only be produced if additional LTFU PK storage samples since the last analysis data cut are planned to be analysed. | EOS |
| 4.16 | 4.15 | NA | Pharmacokinetic | 207966/primary_06/ F4.16 | Median Evaluable Plasma CAB Trough PK Concentration (ug/mL) - Time Plots by Treatment and Strata (Linear and Semi-Log) | | W48, W96 |
| 4.17 | 4.16 | NA | Pharmacokinetic | 207966/primary_06/ F4.17 | Median Evaluable Plasma RPV Trough PK Concentration (ng/mL) - Time Plots by Treatment and Strata (Linear and Semi-Log) | | W48, W96 |

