| 59 | 59 | 59 | Safety | 201584/primary_01/L64 | Listing of ALT, AST, Bilirubin (including Total and Direct Bilirubin), INR, and ALP for Subjects Meeting Hepatobiliary Lab Abnormality Criteria | Remove 'Only Q4W IM Subjects are presented in this listing.' from the footnote. | HL, W48, W96, EOS |
| 60 | 60 | 60 | Safety | 201585/primary | Listing of Investigational Product Exposure | | W48, W96, EOS |

CONFIDENTIAL

207966

| Non-ICH Listings | | | | | | | |
|------------------|------------|------------|-----------------------------|-----------------------|--|---|---------------|
| No. in W48 | No. in W96 | No. in EOS | Population | IDSL / Example Shell | Title | Programming Notes | Deliverable |
| | | | | y_02/L63 | Data for Subject Receiving Oral Bridging | | |
| 61 | 61 | 61 | Safety | 201584/primary_01/L66 | Listing of Dosing Errors and IP Device Malfunctions | | W48, W96, EOS |
| Virology | | | | | | | |
| 62 | 62 | 62 | Confirmed Virologic Failure | 201585/primary_02/L64 | Listing of Replication Capacity in IN and PR/RT Region | Remove 'of Maintenance Phase' from the column header 'Study Day of Maintenance Phase'. | W48, W96, EOS |
| NA | 63 | 63 | Safety | 207966/primary_03/L1 | Listing of Resistance Associated Mutations (Pre-specified INSTI and IAS-USA NNRTI) | Remove "Excluded from PRC (Yes/No) from the first left column; remove the second left column; remove Study Day; mutations are per definition in Section 15.6.7. | W96, EOS |
| PK | | | | | | | |
| 63 | 69 | 69 | Long-term Follow-up | 207966/primary_02/L63 | Listing of Plasma PK Concentration-Time Data since Last Injection | For WK96 and EOS: Remove age and add LTFU oral RPV start date; add asterisk to RPV concentration taken on/after the start of LTFU oral RPV and add a footnote explaining the asterisk, will be produced only if additional LTFU PK storage samples since last analysis data cut are planned to be analysed. | W48, W96, EOS |

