| 4.8 | Long-term Follow-up | 207966/primary_15/T4.2 | Summary of Plasma RPV PK Concentration (ng/mL) - Time Data by Treatment and Visit (Long-term Follow-up Phase) - Including Log-transformed Statistics | Remove the column 'Pl. Time' and the second footnote. | W152 |

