| 4.10 | Pharmacokinetic | 207966/primary_15/F4.10 | Median (5th and 95th Percentile) Plasma RPV Concentration-Time Plots (Linear and Semi-Log) – Maintenance + Extension Phase | Similar notes to above. | W152 |
| 4.11 | Pharmacokinetic | 207966/primary_15/F4.11 | Median (5th and 95th Percentile) Evaluable Plasma CAB Concentration-Time Plots (Linear and Semi-Log) – Maintenance + Extension Phase | Similar notes to above. | W152 |
| 4.12 | Pharmacokinetic | 207966/primary_15/F4.12 | Median (5th and 95th Percentile) Evaluable Plasma RPV Concentration-Time Plots (Linear and Semi-Log) – Maintenance + Extension Phase | Similar notes to above. | W152 |
| 4.13 | Pharmacokinetic | 207966/primary_15/F4.13 | Median (5th and 95th Percentile) Evaluable Plasma CAB Concentration-Time Plots by Strata (Linear and Semi-Log) – Maintenance + Extension Phase | Similar notes to above. | W152 |
| 4.14 | Pharmacokinetic | 207966/primary_15/F4.14 | Median (5th and 95th Percentile) Evaluable Plasma RPV Concentration-Time Plots by Strata (Linear and Semi-Log) – Maintenance + Extension Phase | Similar notes to above. | W152 |

| Pharmacokinetic Figures | | | | | |
|-------------------------|---------------------|-------------------------|--|--|-------------|
| No. in W152 | Population | IDSL / Example Shell | Title | Programming Notes | Deliverable |
| 4.15 | Pharmacokinetic | 207966/primary_15/F4.15 | Median Evaluable Plasma CAB Trough PK Concentration (ug/mL) - Time Plots by Treatment and Strata (Linear and Semi-Log) – Maintenance + Extension Phase | Similar notes to above. | W152 |
| 4.16 | Pharmacokinetic | 207966/primary_15/F4.16 | Median Evaluable Plasma RPV Trough PK Concentration (ng/mL) - Time Plots by Treatment and Strata (Linear and Semi-Log) – Maintenance + Extension Phase | Similar notes to above. | W152 |
| 4.17 | Long-term Follow-up | 207966/primary_02/F4.15 | Plasma PK Concentration-Time since Last Injection Plots by Overall and Strata | Add plot for overall. Exclude RPV concentrations on/after the start of oral RPV that was received after the last injection. Add a footnote: "Note: For subjects who received oral RPV after the last injection, the RPV concentrations taken on or after the start of such oral RPV are excluded from the plot." | W152 |

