|-------------------------|-------------------|-----------------------------|--------------|--|--------------------|
| No. in W152 | Population | IDSL / Example Shell | Title | Programming Notes | Deliverable |
| | | | | second column from the left; add asterisk to RPV concentration taken on/after the start of such oral RPV. and add a footnote, "Note: the RPV concentrations marked with an asterisk were taken on/after the start date of the oral RPV." | |

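### The long-term follow-up RPV summary tables state no exclusion for samples taken on or after the start of oral RPV, although the matching figures exclude them and the listings flag them

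*SAP*

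**What the plan says.** **Tables.** At Week 152, Table 4.8 (Section 15.15.6.6) is titled "Summary of Plasma RPV PK Concentration (ng/mL) - Time Data by Treatment and Visit (Long-term Follow-up Phase) - Including Log-transformed Statistics". Its whole programming note is "Remove the column 'Pl. Time' and the second footnote". At Week 96 and End of Study, Table 4.10/4.2 (Section 15.15.5.6) is titled "Summary of Plasma RPV PK Concentration (ng/mL) -Time Data by Treatment and Visit (Long-term Follow-up Phase) - Including Log-transformed Statistics". Its note makes the same layout change and adds a production condition: "Produce only if we have additional LTFU samples planned to be analysed since last analysis data cut". All three use the Long-term Follow-up population.

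**Figures.** For the same population, Week 152 Figure 4.17 (Section 15.15.6.7) says "Exclude RPV concentrations on/after the start of oral RPV that was received after the last injection" and supplies a footnote telling the reader so. Figure 4.17 at Week 96 and Figure 4.1 at End of Study (Section 15.15.5.7) say "exclude RPV concentrations on/after the start of LTFU oral RPV and add footnote for this exclusion".

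**Listings.** Listing 69 at Week 96 and End of Study (Section 15.15.5.14) says "add asterisk to RPV concentration taken on/after the start of LTFU oral RPV". Week 152 Listing 51 (Section 15.15.6.13) says "add asterisk to RPV concentration taken on/after the start of such oral RPV". Both also add the oral RPV start date.

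**The concern.** Section 2.3 has participants who stop the injections enter LTFU and start HAART for 52 weeks after the last dose. The figure and listing notes show that the sponsor expects some of these regimens to contain oral RPV. From the first tablet on, a plasma RPV value no longer reflects the last injection alone. The sponsor acted on this in the figures and listings, but the instruction does not appear in the tables that give the numbers.

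At stake is how the LTFU RPV summaries are read. A reader who takes the tabulated values as what remains after the last Q4W or Q8W injection would be reading a mixture wherever such samples exist. The table and the figure in one report could then rest on different sets of RPV values, with nothing at the table to say so.

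**Working it through.** The plan gives no figure to reproduce, so the check is a cross-reading, followed by an illustration under stated assumptions.

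**Step 1. RPV samples on or after the oral RPV start, by display.**

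| Display | Week 96 / End of Study | Week 152 |
|---|---|---|
| LTFU RPV table | 4.10 / 4.2: nothing stated | 4.8: nothing stated |
| LTFU figure | 4.17 / 4.1: excluded, with footnote | 4.17: excluded, with footnote |
| LTFU listing | 69 / 69: asterisk and footnote | 51: asterisk and footnote |

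At Week 48 no LTFU RPV table is planned, so the question does not arise there.

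**Step 2. Does a general rule cover the tables?** Section 15.6.5 was checked for each candidate.
- It sets up two summaries, all data and evaluable data. The exclusion for dosing errors and oral bridging belongs to the evaluable set. The three table titles do not say evaluable, they are built on the T4.2 shells (the all-data RPV table) rather than T4.4 (the evaluable one), and no evaluable LTFU table is planned.
- That exclusion names oral bridging. Table 19 starts LTFU after the later of the last injection and the end of the last oral bridging, and Table 2 treats LTFU ART as a separate category.
- The LTFU evaluable windows depend only on days since the last injection.
- The exclusions for same-day post-dose samples in the main study and for liver-event samples do not reach these values.

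No rule in the SAP supplies the missing exclusion.

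**Step 3. Is the wording the same across time points?** No. Week 96 and End of Study refer to LTFU oral RPV; Week 152 refers to oral RPV received after the last injection. These can differ for a participant whose last study treatment was oral CAB+RPV bridging: that RPV came after the last injection but is not LTFU therapy.

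**Step 4. Illustration of size.** Suppose a share p of the samples at one visit is raised k-fold by oral RPV, and the underlying level g is otherwise the same. Then

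log(GM) = (1 − p)·log g + p·log(k·g) = log g + p·log k,

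so the geometric mean is multiplied by k^p. Both p and k are assumptions; the SAP gives neither.

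| k | p | k^p |
|---|---|---|
| 2 | 5% | 1.04 |
| 3 | 10% | 1.12 |
| 3 | 20% | 1.25 |
| 3 | 40% | 1.55 |
| 5 | 20% | 1.38 |
| 10 | 10% | 1.26 |
| 10 | 20% | 1.58 |
| 10 | 40% | 2.51 |

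The table shows only how the effect depends on two unknowns. It does not estimate what the trial's tables contain.

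**The case against.** The best defence is that the displays serve different ends. The figure plots concentration against time since the last injection, so tablet-derived drug plainly does not belong there. The table summarises plasma RPV by treatment and visit, and an all-data summary keeps imperfect samples by design. The affected values are also disclosed in the listings, and the mock shells, which might carry a footnote, are not part of the SAP.

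Part of this stands. The SAP never describes the tables as a washout summary, it never instructs that these values be kept, and the shells are unseen. Disclosure in the listings also makes this less than a hidden problem. But Section 15.6.5 defines all data as disregarding sample timing; it says nothing about a second source of the drug. The LTFU figures are not labelled evaluable either, yet they exclude these values. The Week 152 CAB table (4.7) carries the same note as the RPV table, which suggests that the RPV-specific step was not considered. If keeping the values is intended, no specified table footnote says so.

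A reader might infer more than the SAP supports:
- *Upward bias at every LTFU visit.* Only visits with samples taken after oral RPV starts are affected. The first window, LTFU Month 1/WD (LTFU days 1 to 63, Table 14), also takes withdrawal-visit data, and samples drawn before any oral RPV are unaffected.
- *A distorted Q8W versus Q4W result.* The tables show both arms, but no LTFU test or model is planned. The PK models in Section 9.3 concern steady-state troughs and the thigh sub-study.
- *A compromised endpoint.* The listed PK endpoints are Ctrough, post-dose concentration and AUC; LTFU concentrations are not among them.

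**Conclusion.** The point holds as an inconsistency between displays. The three LTFU RPV tables lack an exclusion that the plan itself applies to the figures for the same population, and no other rule provides it. Run as written, the descriptive RPV statistics would pool oral and residual long-acting RPV at any LTFU visit with such samples, and could disagree with the figure.

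The size cannot be stated: it is nil where no participant took oral RPV after the last injection, and otherwise depends on an unknown share and unknown levels. The conclusion assumes that the unseen shells carry no such exclusion. That is likely, since the named shell is a Maintenance-phase all-data table, but it is not proven. The Week 96 and End of Study tables may not be produced at all; Week 152 Table 4.8 carries no such condition. The consequence is limited to a descriptive PK summary.

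**What to change.** Add to the programming notes of Table 4.10 (Week 96), Table 4.8 (Week 152) and Table 4.2 (End of Study), where they are produced, the exclusion and footnote already written for Week 152 Figure 4.17. Alternatively, keep the samples but summarise those taken on oral RPV in a separate row, so that nothing is lost. In either case, use one wording for the oral RPV start in the tables, figures and listings at all three time points, and let it settle the oral-bridging case in Step 3. If any of these tables has already been issued, a footnote giving the number of affected samples per visit would serve.

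The programming cost is small, because the oral RPV start date is already needed for the figure and the listing. The statistical cost of exclusion is a smaller n at the affected visits, by exactly the share of samples taken on oral RPV: under the 40% assumption above, 40% of that visit's RPV samples. If the share proves large, the separate row is the better choice.

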15.15.6.7. Pharmacokinetic Figures

| Pharmacokinetic Figures | | | | | |
|-------------------------|-----------------|------------------------|---|--|-------------|
| No. in W152 | Population | IDSL / Example Shell | Title | Programming Notes | Deliverable |
| 4.1 | Pharmacokinetic | 207966/primary_15/F4.1 | Individual Plasma CAB Concentration-Time Plots (Linear and Semi-Log) – Maintenance + Extension Phase | | W152 |
| 4.2 | Pharmacokinetic | 207966/primary_15/F4.2 | Individual Plasma RPV Concentration-Time Plots (Linear and Semi-Log) – Maintenance + Extension Phase | | W152 |
| 4.3 | Pharmacokinetic | 207966/primary_15/F4.3 | Mean (SD) Plasma CAB Concentration-Time Plots (Linear and Semi-Log) – Maintenance + Extension Phase | Treat Week 152 similarly to Week 96 on X axis and update the relevant footnote as “To save the plotting space, Week 96 is displayed next to Week 48 and Week 152 is displayed next to Week 152, with hashes to indicate the X axis break.” | W152 |
| 4.4 | Pharmacokinetic | 207966/primary_15/F4.4 | Mean (SD) Plasma RPV Concentration-Time Plots (Linear and Semi-Log) – Maintenance + Extension Phase | Similar notes to above. | W152 |
| 4.5 | Pharmacokinetic | 207966/primary_15/F4.5 | Mean (SD) Evaluable Plasma CAB Concentration-Time Plots (Linear and Semi-Log) – Maintenance + Extension Phase | Similar notes to above. | W152 |
| 4.6 | Pharmacokinetic | 207966/primary_15/F4.6 | Mean (SD) Evaluable Plasma RPV Concentration-Time Plots (Linear and Semi-Log) – Maintenance + Extension Phase | Similar notes to above. | W152 |
| 4.7 | Pharmacokinetic | 207966/primary_15/F4.7 | Mean (SD) Evaluable Plasma CAB Concentration-Time Plots by Strata (Linear and Semi-Log) – Maintenance + Extension | Similar notes to above. | W152 |

| Pharmacokinetic Figures | | | | | |
|-------------------------|-----------------|-------------------------|--|-------------------------|-------------|
| No. in W152 | Population | IDSL / Example Shell | Title | Programming Notes | Deliverable |
| | | | Phase | | |
| 4.8 | Pharmacokinetic | 207966/primary_15/F4.8 | Mean (SD) Evaluable Plasma RPV Concentration-Time Plots by Strata (Linear and Semi-Log) – Maintenance + Extension Phase | Similar notes to above. | W152 |
| 4.9 | Pharmacokinetic | 207966/primary_15/F4.9 | Median (5th and 95th Percentile) Plasma CAB Concentration-Time Plots (Linear and Semi-Log) – Maintenance + Extension Phase | Similar notes to above. | W152 |
| 4.10 | Pharmacokinetic | 207966/primary_15/F4.10 | Median (5th and 95th Percentile) Plasma RPV Concentration-Time Plots (Linear and Semi-Log) – Maintenance + Extension Phase | Similar notes to above. | W152 |
| 4.11 | Pharmacokinetic | 207966/primary_15/F4.11 | Median (5th and 95th Percentile) Evaluable Plasma CAB Concentration-Time Plots (Linear and Semi-Log) – Maintenance + Extension Phase | Similar notes to above. | W152 |
| 4.12 | Pharmacokinetic | 207966/primary_15/F4.12 | Median (5th and 95th Percentile) Evaluable Plasma RPV Concentration-Time Plots (Linear and Semi-Log) – Maintenance + Extension Phase | Similar notes to above. | W152 |
| 4.13 | Pharmacokinetic | 207966/primary_15/F4.13 | Median (5th and 95th Percentile) Evaluable Plasma CAB Concentration-Time Plots by Strata (Linear and Semi-Log) – Maintenance + Extension Phase | Similar notes to above. | W152 |
| 4.14 | Pharmacokinetic | 207966/primary_15/F4.14 | Median (5th and 95th Percentile) Evaluable Plasma RPV Concentration-Time Plots by Strata (Linear and Semi-Log) – Maintenance + Extension Phase | Similar notes to above. | W152 |

| Pharmacokinetic Figures | | | | | |
|-------------------------|---------------------|-------------------------|--|--|-------------|
| No. in W152 | Population | IDSL / Example Shell | Title | Programming Notes | Deliverable |
| 4.15 | Pharmacokinetic | 207966/primary_15/F4.15 | Median Evaluable Plasma CAB Trough PK Concentration (ug/mL) - Time Plots by Treatment and Strata (Linear and Semi-Log) – Maintenance + Extension Phase | Similar notes to above. | W152 |
| 4.16 | Pharmacokinetic | 207966/primary_15/F4.16 | Median Evaluable Plasma RPV Trough PK Concentration (ng/mL) - Time Plots by Treatment and Strata (Linear and Semi-Log) – Maintenance + Extension Phase | Similar notes to above. | W152 |
| 4.17 | Long-term Follow-up | 207966/primary_02/F4.15 | Plasma PK Concentration-Time since Last Injection Plots by Overall and Strata | Add plot for overall. Exclude RPV concentrations on/after the start of oral RPV that was received after the last injection. Add a footnote: "Note: For subjects who received oral RPV after the last injection, the RPV concentrations taken on or after the start of such oral RPV are excluded from the plot." | W152 |

15.15.6.8. Pharmacokinetic / Pharmacodynamic Figures

| Pharmacokinetic / Pharmacodynamic Figures | | | | | |
|---|-----------------|------------------------|---|---|-------------|
| No. in W152 | Population | IDSL / Example Shell | Title | Programming Notes | Deliverable |
| PK / PD Efficacy Analyses | | | | | |
| 5.1 | Pharmacokinetic | 207966/primary_15/F5.1 | Individual CAB Trough Concentration-time Profiles for Subjects with Snapshot 'HIV-1 RNA ≥ 50 c/mL' at Week 152 and Median, 5th & 95th Percentile of CAB Conc-Time Profiles for Other Subjects (Semi-Log) – Maintenance + Extension Phase | | W152 |
| 5.2 | Pharmacokinetic | 207966/primary_15/F5.2 | Individual RPV Trough Concentration-time Profiles for Subjects with Snapshot 'HIV-1 RNA ≥ 50 c/mL' at Week 152 and Median, 5th & 95th Percentile of RPV Conc-Time Profiles for Other Subjects (Semi-Log) – Maintenance + Extension Phase | | W152 |
| PK / PD Safety Analyses | | | | | |
| 5.3 | Pharmacokinetic | 207966/primary_02/F5.6 | Scatter Plot of Maximum Change from Baseline in ALT versus Last Trough CAB PK Concentrations by Strata and Treatment during the Maintenance and Extension Phase | Replace "Maintenance" with "Maintenance and Extension" in the first footnote. | W152 |
| 5.4 | Pharmacokinetic | 207966/primary_02/F5.7 | Scatter Plot of Maximum Change from Baseline in ALT versus Last Trough RPV PK Concentrations by Strata and Treatment during the Maintenance and Extension Phase | Replace "Maintenance" with "Maintenance and Extension" in the first footnote. | W152 |
| 5.5 | Pharmacokinetic | 207966/primary_02/F5.8 | Scatter Plot of Maximum Change from Baseline in Total Bilirubin versus Last Trough CAB PK Concentrations by Strata and Treatment during the Maintenance and Extension Phase | Replace "Maintenance" with "Maintenance and Extension" in the first footnote. | W152 |

| Pharmacokinetic / Pharmacodynamic Figures | | | | | |
|---|-----------------|-------------------------|---|---|-------------|
| No. in W152 | Population | IDSL / Example Shell | Title | Programming Notes | Deliverable |
| 5.6 | Pharmacokinetic | 207966/primary_02/F5.9 | Scatter Plot of Maximum Change from Baseline in Total Bilirubin versus Last Trough RPV PK Concentrations by Strata and Treatment during the Maintenance and Extension Phase | Replace "Maintenance" with "Maintenance and Extension" in the first footnote. | W152 |
| 5.7 | Pharmacokinetic | 207966/primary_02/F5.13 | Scatter Plot of Change from Baseline in Pre-dose QTcF versus CAB Trough PK Concentration at Week 152 by Treatment | Adjust the alignment of the footnote. | W152 |
| 5.8 | Pharmacokinetic | 207966/primary_02/F5.14 | Scatter Plot of Change from Baseline in Pre-dose QTcF versus RPV Trough PK Concentration at Week 152 by Treatment | Adjust the alignment of the footnote. | W152 |

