| Design Features | 
 Study 207966 (Antiretroviral Therapy as Long Acting Suppression every 2 Months-ATLAS-2M) is a Phase IIIb, randomized, open-label, active-controlled, multicenter, parallel-group, non-inferiority study designed to assess the antiviral activity and safety of CAB LA + RPV LA administered every 4 weeks compared CAB LA + RPV LA administered every 8 weeks in approximately 1020 adult HIV-1 infected patients. The ATLAS-2M main study comprises a Screening Phase (up to 35 days), and a Maintenance Phase (Day 1 to Week 100), followed by an Extension Phase (post Week 96). Additionally, any participant who receives at least a single dose of CAB LA and/or RPV LA and discontinues the CAB LA + RPV LA regimen will enter the Long-term Follow-up Phase and will initiate highly active antiretroviral therapy (HAART) for 52 weeks after the last dose of CAB LA and/or RPV LA, or until the assigned CAB LA + RPV LA regimen is locally approved and commercially available. Two groups of patients who fulfill eligibility requirements will be randomized (1:1) at Day 1 in the main study to receive CAB LA + RPV LA Q4W, or CAB LA + RPV LA Q8W regimen for at least 100 weeks: 
 Group 1: Patients randomized from current ART Standard of Care (SOC) therapy Group 2: Patients currently receiving CAB LA + RPV LA Q4W After a minimum of 152 weeks on the ATLAS-2M main study, approximately 82 (41 per treatment arm) eligible participants will be enrolled in the sub-study. The enrolled sub-study participants will receive the study treatment on the same frequency as their randomized treatment, for example, participants randomized to the Q8W treatment in the main study will continue receiving the study treatment in every 8 weeks in the sub-study. The ATLAS-2M sub-study will consist of three phases including a Screening Phase (1 injection interval: 4 weeks for Q4W participants and 8 weeks for Q8W participants), a Thigh Injection Phase with 16 weeks of thigh injections (4 injection intervals for Q4W participants and 2 injection intervals for Q8W participants) and a Return to Gluteal Injection Phase with 8 weeks of gluteal injections for both Q4W and Q8W participants. At the conclusion of the sub-study, participants will have the option to continue on the A2M main study or if commercial access treatment is available, the participants can transition off the sub-study and withdraw from ATLAS-2M and proceed directly to CAB/RPV LA. |

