5.2. Baseline Definitions

For all endpoints (except as noted in baseline definitions) the baseline value will be the latest pre-treatment (see [Table 8](#)) assessment with a non-missing value, including those from unscheduled visits. ‘Pre-treatment’ in main study refers to prior to the study treatment (i.e. CAB and/or RPV) in this study, and ‘pre-treatment’ in sub-study refers to prior to the first CAB and/or RPV thigh injection.

Electrocardiograms (ECGs) are to be performed in triplicate on main study Day 1 visit. The baseline value for an ECG parameter will be the mean of the last pre-treatment set of assessments from the same date, so long as at least one of the triplicate assessments is available.

Unless otherwise stated, if baseline data is missing no derivation will be performed and baseline will be set to missing.

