11.1. Overview of Planned Analyses

Table 6 provides an overview of the planned analyses with full details being presented in Appendix 15: List of Data Displays. All PK displays will be based on the PK Population, unless otherwise specified.

Table 6 Overview of Planned Pharmacokinetic / Pharmacodynamic Analyses

| | Stats Analysis | | | Summary | | Individual | |
|---|----------------|---|---|---------|---|------------|---|
| | T | F | L | T | F | F | L |
| CAB/RPV Week 8 concentrations by snapshot 'HIV-1 RNA \geq 50 c/mL' (Yes vs. No) at Week 48 for participants without prior exposure to CAB+RPV | | | | Y | Y | | |
| Analysis of snapshot 'HIV-1 RNA \geq 50 c/mL' at Week 48 by Week 8 trough concentration, and subgroup [1] – univariable analysis /multivariable analysis for participants without prior exposure to CAB+RPV | Y | | | | | | |
| Individual CAB/RPV concentration-time profiles for participants with snapshot 'HIV-1 RNA \geq 50 c/mL' at Week 48 or 96 or 152 | | | | | Y | | |
| Maximum change from baseline in ALT/Total Bilirubin versus last trough CAB/RPV concentrations for Week 48 and Week 152 analyses[2] | | | | | Y | | |
| Change from baseline in pre-dose QTcF versus CAB/RPV concentrations at Week 48 or 152 | | | | | Y | | |
| Maximum toxicity grades of most frequently reported study drug ISR AEs [3] versus last trough CAB/RPV PK concentrations for Week 48 analysis[2] | | | | | Y | | |

NOTES:

- T = Table, F = Figure, L = Listings, Y = Display generated.
- Stats Analysis = Represents TFL related to any formal statistical analyses (i.e. modelling) conducted.
- Summary = Represents TF related to any summaries (i.e. descriptive statistics) of the observed raw data.
- Individual = Represents FL related to any displays of individual participant observed raw data.

1. Refer to Section [11.2](#).
2. Display by rederived randomization strata, i.e. prior exposure to CAB+RPV (0, 1-24, >24 weeks) derived based on eCRF.
3. Most frequently reported study drug ISR AEs are those top 5 in incidence in either treatment arm (i.e. Q8W or Q4W arm).

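### The Week 152 QTcF-versus-trough plots (Figures 5.7 and 5.8) mix participants whose baseline ECG preceded CAB+RPV with participants whose baseline ECG was taken on it, and should be split by prior exposure

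*SAP*

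**What the plan says.** Section 15.15.6.8 lists two Week 152 figures: 5.7, "Scatter Plot of Change from Baseline in Pre-dose QTcF versus CAB Trough PK Concentration at Week 152 by Treatment", and 5.8, "Scatter Plot of Change from Baseline in Pre-dose QTcF versus RPV Trough PK Concentration at Week 152 by Treatment". The matching row of Table 6 in Section 11.1 reads "Change from baseline in pre-dose QTcF versus CAB/RPV concentrations at Week 48 or 152". It is marked for a figure only.

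Section 5.2 sets the baseline: pre-treatment "in main study refers to prior to the study treatment (i.e. CAB and/or RPV) in this study". For ECGs, "The baseline value for an ECG parameter will be the mean of the last pre-treatment set of assessments from the same date". Section 2.3 describes two entry groups, one coming from standard-of-care ART and the other being "Group 2: Patients currently receiving CAB LA + RPV LA Q4W". Section 5.1 pools participants with and without oral lead-in inside each treatment column. The PK population in Section 4 has no restriction on prior exposure.

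Note 2 of Table 6 says "Display by rederived randomization strata, i.e. prior exposure to CAB+RPV (0, 1-24, >24 weeks) derived based on eCRF". It is attached to the ALT/bilirubin row and the ISR-grade row, but not to the QTcF row. Accordingly, Figures 5.3 to 5.6 (ALT and bilirubin) are titled by strata and treatment, and Figures 5.7 and 5.8 by treatment only.

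**The concern.** A change from baseline plotted against concentration is normally read as change from an off-drug state. For participants arriving on CAB LA + RPV LA that reading fails, because the last ECG before study drug in this trial was recorded with both drugs already on board. A plot that does not separate them from participants starting the drugs shows a blend of two quantities under one label.

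QTc prolongation (at supratherapeutic doses) is listed in Table 4 as an adverse event of special interest for RPV. If a QTcF effect exists, the blend errs toward looking smaller than it is, which is the wrong direction for a safety display.

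**Working it through.** The SAP states no slope, effect size or precision for these plots, so there is no planned figure to reproduce. The check has two parts.

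**1. Is the baseline ECG on-drug for some participants?**
- Section 5.2 counts only CAB/RPV given in this study when it defines pre-treatment.
- Section 2.3 has Group 2 entering on Q4W injections and continuing by injection from Day 1, with no oral lead-in.
- The schedule of activities (Section 15.2.1, note r) plans a Day 1 pre-dose PK sample for participants from the ATLAS Q4W arm. Section 15.6.5 calls that sample evaluable at 24 to 32 days after the last injection. The plan thus expects measurable drug at the visit that supplies the baseline ECG.

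So yes: for these participants the baseline ECG is an on-treatment trough ECG.

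**2. What does pooling do?**

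Take change in QTcF = b × (C152 − C0) + error. Here b is the true effect per unit of trough, C152 is the Week 152 trough and C0 the baseline trough. C0 is zero for participants new to the drugs and positive for the pre-exposed. Let f be the pre-exposed share and ρ the within-person correlation between baseline and Week 152 troughs. None of b, f, ρ or the trough levels is in the SAP, so all are assumptions shown over a range. Concentrations are scaled to a mean Week 152 trough of 1.

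*Level of change*, equal mean troughs: pooled mean = (1 − f) × b + f × 0.
- f = 0.20: 0.80 b
- f = 0.375: 0.625 b, or 0.63 b
- f = 0.50: 0.50 b

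*Slope*, equal means and variances: the pre-exposed slope is b(1 − ρ), so the pooled slope is b(1 − fρ).

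| f | ρ = 0 | ρ = 0.4 | ρ = 0.7 | ρ = 0.9 |
|---|---|---|---|---|
| 0.20 | 1.00 b | 0.92 b | 0.86 b | 0.82 b |
| 0.375 | 1.00 b | 0.85 b | 0.74 b | 0.66 b |
| 0.50 | 1.00 b | 0.80 b | 0.65 b | 0.55 b |

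A simulation (400,000 participants per setting, trough CV 0.4) agrees to about 0.01.

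*Unequal troughs*, f = 0.375, same simulation:
- If the pre-exposed have Week 152 troughs 20% to 40% higher than the others, the pooled slope is 0.76 b to 0.63 b at ρ = 0, and 0.50 b to 0.40 b at ρ = 0.7.
- If their baseline trough was 30% to 50% above their Week 152 trough, which is possible after moving from Q4W to Q8W, their own mean change is −0.3 b to −0.5 b. The pooled mean is then 0.625 − 0.375 × 0.3 = 0.51 b, down to 0.625 − 0.375 × 0.5 = 0.44 b.

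The level is pulled toward zero in every case with f > 0, on-drug baselines and b ≠ 0. The slope need not be: at ρ = 0 with equal mean troughs it is unchanged. Within the 0-week stratum, both level and slope return to 1.00 b if C0 really is zero there.

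**The case against.** The best defence is that nothing inferential rests on these plots. No slope or test is planned for the QTcF row. QT safety is also covered by the Week 152 table of QTc values by category (3.57, which needs no baseline), the 500 msec criterion, the AESI summaries, and ECG listings shown by prior exposure. Randomization was stratified by prior exposure, so on-drug baselines should be similarly frequent in both arms. All of this stands, and it caps the importance of the point.

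The figure shells are not shown and might mark strata by symbol. Another figure (Week 96 Figure 4.17, Section 15.15.5.7) is plotted by treatment with strata colour-coded. That cannot be excluded here, but neither the titles nor Table 6 ask for it, whereas the programming note for Figure 4.17 does.

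Note 2 also covers the ISR-grade plots, which involve no change from baseline. Its absence from the QTcF row therefore does not show that the authors recognised on-drug baselines and then overlooked this row. It shows only that the split is an available layout.

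A further limit concerns RPV. Under Section 15.6.2, 0 weeks counts only CAB+RPV received in ATLAS. Section 5.4.2 allows an NNRTI as the baseline third agent, and Section 15.6.7 lists rilpivirine in that class. The stratum therefore does not by itself guarantee an RPV-free baseline. The SAP does not say whether anyone entered on oral RPV.

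**Conclusion.** The point holds as a minor one. Figures 5.7 and 5.8, and the QTcF row of Table 6, combine changes that include drug initiation with changes that do not. If QTcF responds to the drug, the pooled level of change is too small by the pre-exposed share when mean troughs are equal: 20% to 50% for assumed shares of 20% to 50%.

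Three stronger readings might be inferred and are not supported:
- **That the pre-exposed change cannot contain any drug effect.** It omits the off-drug to on-drug step, but still carries the effect of any trough difference between Day 1 and Week 152.
- **That the plotted relation is diluted by the same percentage as the level.** The slope depends on the within-person trough correlation and on trough differences between groups. It may not be diluted at all, and its size cannot be computed from the SAP.
- **That a trial conclusion is at risk.** These are descriptive safety figures, and no primary or key secondary inference uses them.

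**What to change.** Attach note 2 of Table 6 to the QTcF row, and retitle and panel Figures 5.7 and 5.8 by rederived prior-exposure stratum and treatment, matching Figures 5.3 to 5.6. State that any comment on QTcF and concentration will rest on the 0-week stratum. Add a footnote that 0 weeks refers to CAB+RPV received in ATLAS and does not by itself exclude oral RPV taken earlier as standard of care.

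The stratum variable and the layout already exist, so the cost is re-panelling two figures. The downside is fewer points per panel.
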